16.3 APPENDIX III: ADVERSE EVENTS OF SPECIAL INTEREST: INJECTION SITE REACTIONS

The following table should be used to characterize injection-site reactions and provide appropriate grading of severity (DAIDS and modified additions).

Injection-site Reactions

Parameter	Grade 1 (Mild)	Grade 2 (Moderate)	Grade 3 (Severe)	Grade 4 (Potentially life-threatening)
Injection-site pain	Pain without touching or pain when area is touched: no or minimal limitation of use of limb	Pain without touching or pain when area is touched limiting use of limb OR causing greater than minimal interference with usual social and functional activities	Pain without touching or pain when area is touched causing inability to perform usual social and functional activities	Pain without touching or pain when area is touched causing inability to perform basic self-care function OR hospitalization (other than emergency room visit) indicated for management of pain/tenderness
Characterization of the injection site, if not normal	Erythema OR induration of 5x5 cm - 9x9 cm (or 25 cm ² -81 cm ²)	Erythema OR induration OR Edema >9 cm any diameter (or >81 cm ²)	Ulceration OR secondary infection OR Phlebitis or Sterile abscess OR drainage	Necrosis (involving dermis and deeper tissue)
Pruritus associated with injection	Itching localized to injection site AND relieved spontaneously or <48 hours of treatment	Itching beyond the injection site but not generalized OR itching localized to injection site requiring ≥48 hours treatment	Generalized itching causing inability to perform usual social and functional activities	N/A
Bleeding	Initial bleed that does not exceed bandage and spontaneously stops	Bleeding that exceeds bandage and spontaneously stops	Continued bleeding that requires change of dressing and alternative injection site	N/A
Absorption of drug	Minor elevation of skin at injection site but no leakage of injection material	Leakage at injection site ceases with decrease in injection rate	Leakage at injection site that does not cease with decrease in injection rate	

16.4 APPENDIX V: NEUROLOGICAL ASSESSMENT

Three Question Screening Survey (Simioni, et al, 2010)

1. ‘Do you experience frequent memory loss (e.g. do you forget the occurrence of special events even the more recent ones, appointments, etc.)’?
2. ‘Do you feel that you are slower when reasoning, planning activities, or solving problems’?
3. ‘Do you have difficulties paying attention (e.g. to a conversation, a book, or a movie)’?

For each question, subjects should provide one of the following answers: ‘never’, ‘hardly ever’, or ‘yes, definitely’.

If subject answers “yes, definitely” to any question, Investigator may use additional neurological assessment modalities at its discretion.

1. INTRODUCTION

This Statistical Analysis Plan describes the planned analyses and reporting for the clinical trial protocol PRO 140_CD01-Extension, sponsored by CytoDyn Inc. The reader of this Statistical Analysis Plan (SAP) is encouraged to review the complete protocol and amendments as this plan contains only a limited overview of protocol information. The main objective of this plan is to provide details pertaining to statistical methodology, data conventions, and processes used for the analysis of data from this trial.

The format and content of this Statistical Analysis Plan are structured to provide sufficient detail to meet the requirements specified by the International Conference on Harmonization (ICH) E9: Guidance on Statistical Principles in Clinical Trials. All work planned and presented in this Statistical Analysis Plan will follow the ethical guidelines published by the American Statistical Association (ASA).

The following documents were reviewed in preparation of this Statistical Analysis Plan:

- Version 4.0, protocol 13 May 2019
- ASA Ethical Guidelines for Statistical Practice (2016)
- The Royal Statistical Society: Code of Conduct (2014)
- ICH Guidance on the Structure and Content of Clinical Study Reports (ICH E3, 1996)
- ICH Guidance on the Structure and Content of Clinical Study Reports (ICH E3(R1), 2013)
- ICH Guidance on the Statistical Principles for Clinical Trials (ICH E9, 1998)
- ICH Guidance on the Statistical Principles for Clinical Trials (ICH E9(R1), 2017)

2. PROTOCOL DESIGN AND OBJECTIVES

2.1 Study Objectives

The primary objective is to provide PRO 140 on a continued basis to subjects who complete participation in PRO140_CD02 or CD02_OpenLabel and would require continued access to PRO 140 to form a viable regimen, in the opinion of the treating physician.

Study Center: Up to 10 centers in the United States. Centers must have the capability of implementing appropriate infection-control measures to prevent infection of study staff and others who share the clinical site space.

2.2 Design Overview

This is an extension study, to provide continued access to PRO 140 to subjects who complete participation in PRO140_CD02 or CD02_OpenLabel and continue to receive clinical benefit and would require PRO 140 to form a viable regimen, in the opinion of the treating physician. The patient population for this trial is treatment-experienced HIV-infected patients with CCR5-tropic virus who demonstrate evidence of HIV-1 suppression after successfully completed 24 weeks of treatment in the PRO140_CD02 or CD02_Open Label study.

PRO 140 700 mg is administered as subcutaneous injection in the abdomen weekly. A total of 700 mg (175 mg/mL) is delivered as two 2 mL injections on opposite sides of the abdomen. Subjects who were enrolled under a previous Protocol version and are still receiving the 350 mg dose, have the option of increasing their dose to 700mg for the remainder of the Treatment Extension Phase to provide maximum viral load suppression in a heavily treatment experienced population to avoid developing resistance to current OBT therapies. .

NOTE: Alternatively, the 700 mg dose may be delivered as four 1mL doses (two SC injections on opposite sides of abdomen) for those that experience discomfort with the 2mL injections (i.e. subjects with low body fat percentages).

The study will have three phases: Screening Phase, Treatment Extension Phase and Follow-up Phase as shown in the study flow diagram **Figure 2-1**.

Screening Phase (up to 21days):

This phase is designed to determine whether subjects are eligible to proceed to the Treatment Phase of the study. This phase consists of a series of assessments designed to determine eligibility. A written informed consent from the subject will be obtained by the Investigator or suitably qualified individual before the performance of any protocol-specific procedure.

All subjects will continue taking PRO 140 along with OBT during the Screening Phase.

NOTE: Subject consent and screening assessments should be completed prior to EOT visit in the PRO140_CD02 or CD02_OpenLabel study.

Treatment Extension Phase:

The Treatment Extension Phase begins with an evaluation of most recent laboratory results (viral load & CD4 count) obtained in PRO140_CD02 or CD02_OpenLabel study. All subjects who fail to meet eligibility criteria will be considered screen failures and exit the study without further evaluation. Subjects who meet all eligibility criteria will receive first treatment injection at Treatment Extension (TE) Visit 1 (which corresponds to EOT from PRO140_CD02 or CD02_OpenLabel study).

The Treatment Extension Phase consists of weekly treatment injections of PRO140 700mg* SC in addition to OBT. Optimized background therapy (OBT) is a standard-of-care regimen comprised of 3 or more antiretroviral agents selected by the Investigator based on treatment history and genotypic and/or phenotypic assessments. Subjects will continue the same OBT regimen initiated within the PRO140_CD02 or CD02_OpenLabel study.

NOTE: Subjects enrolled prior to Protocol v4.0 may still be receiving the original 350mg dose and have the option of increasing their dose to 700mg.

As shown in Table 0-1, all subjects will receive PRO 140 SC injection and Optimized Background Therapy.

The injectable study treatment (PRO 140) will be administered:

- by a qualified medical professional (MD, DO, PA, LPN, LVN, NP, RN, or CMA if permitted by state law) or
- self-administered by subjects

Study participants will be monitored every 4 weeks for viral load and CD4 count. Should subjects experience virologic failure, they will be allowed to continue PRO 140 with existing OBT regimen while waiting for new regimen to be constructed by the Investigator.

Virologic failure is defined two consecutive HIV-1 RNA levels \geq 400 copies/mL.

[figure not shown]
Subjects who experience virologic failure at any point during the Treatment Extension Phase will undergo the Virologic Failure (VF) Visit assessments and then return in 4 weeks (\pm allowed window) for the Safety Follow-up Visits.

Safety Follow-up Visit:

Duration of the Follow-up Phase is determined upon whether or not subject has experienced virologic failure during the Treatment Extension Phase.

- Subjects who experience virologic failure within Treatment Extension Phase will be followed up every 4 weeks until viral suppression is achieved (i.e., plasma HIV-1 RNA levels below level of detection) or up to a maximum of 6 months after cessation of therapy if the treating physician does not feel that there is an antiretroviral regimen that will regain full viral suppression.
- Subjects who do not experience virologic failure at the end of Treatment Extension Phase, will be followed up every 2 weeks for total of 4 weeks.

Figure 2-1 Clinical Trial Flow Diagram

Study Duration

- **Screening Phase:**
 - up to 21 days
- **Treatment Extension Phase:**
 - weekly (\pm allowed windows) until subject withdraws consent, experience virologic failure or PRO 140 is approved or CytoDyn decides to discontinue its development
- **Follow-up Phase:**
 - weeks* (\pm allowed windows)
*or up to maximum of 6 months after experiencing Virologic Failure (VF) if the treating physician does not feel that there is an antiretroviral regimen that will regain full viral suppression.

2.3 Study Treatment

2.3.1 Treatment Group

This is a single arm study. All eligible subjects will receive PRO 140 SC injection and Optimized Background Therapy . PRO 140 as a 350mg dose (per protocol prior to v4.0) or 700mg (per protocol after v4.0) subcutaneous injection weekly until one of the following occurs:

- Virologic failure
- Consent withdrawn
- PRO 140 is approved
- CytoDyn decides to discontinue its development

NOTE: Subjects enrolled prior to Protocol v4.0 may still be receiving the original 350mg dose and have the option of increasing their dose to 700mg.

Study Drug	Dosage Form	IP concentration	Dosing Frequency and Amount	Route of Administration
PRO 140 350mg	Parenteral solution	175 mg/mL	2 injections of PRO 140 (2 X 1 mL/inj.) for 48 weeks	SC injection
			for 48 weeks	

PRO 140 700mg		Parenteral solution	175 mg/mL	2 injections of PRO 140 (2 X 2 mL/inj.) for 48 weeks	SC injection
---------------	--	---------------------	-----------	--	--------------

2.3.2 Randomization and Blinding

No blinding or randomization requirement.

2.4 Study Outcome Measures

- Mean change in viral load (HIV-1 RNA levels) at the conclusion of treatment period
- Mean change in CD4 cell count at the conclusion of treatment period
- Emergence of Dual/Mixed (D/M)- and CXCR4-tropic virus in patients who had exclusive CCR5-tropic virus at study entry.
- Tolerability of repeated subcutaneous administration of PRO 140 as assessed by investigator-evaluation of injection site reactions
- Frequency of treatment-related adverse events resulting in study drug discontinuation
- Frequency of Grade 3 or 4 adverse events as defined by the DAIDS Adverse Event scale

3. SAMPLE SIZE DETERMINATION

Sample size determination is not applicable as only those subjects who are currently enrolled in PRO 140_CD 02 or CD02_OpenLabel study are allowed to participate in this study.

4. INTERIM ANALYSIS

There is no planned interim analysis (IA) for this study.

5. ANALYSIS POPULATIONS

5.1 Safety Population

The Safety population is defined as the set of subjects who received at least one dose of PRO 140. This population will be used for the analysis of safety parameters.

6. DATA CONVENTION AND RELATED DEFINITIONS

6.1 Baseline Definition

Baseline for a given parameter or endpoint is defined to be the baseline of CD02 or CD02_OpenLabel study.

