
 ● Follow-up Phase: 
 ○ 4 weeks* (± allowed windows) 
*or up to maximum of 6 months after experiencing Virologic Failure (VF) if the treating physician does not feel that there is an antiretroviral regimen that will regain full viral suppression.
	
Inclusion Criteria: Potential subjects are required to meet all of the following criteria for enrollment into the study.	

 1. Subjects who have completed 24 weeks of treatment in PRO 140_CD 02 or CD02_OpenLabel study, and Investigator believes subject requires continued access to PRO 140 in order to continue deriving clinical benefit and maintain HIV-1 viral suppression 2. HIV-1 RNA ≤ 50 copies/ml at T23 Visit in PRO140_CD02 or CD02_OpenLabel study 3. Both male and female patients and their partners of childbearing potential must agree to use 2 medically accepted methods of contraception (e.g., barrier contraceptives [male condom, female condom, or diaphragm with a spermicidal gel], hormonal contraceptives [implants, injectables, combination oral contraceptives, transdermal patches, or contraceptive rings], and intrauterine devices) during the course of the study (excluding women who are not of childbearing potential and men who have been sterilized). Females of childbearing potential must have a negative urine pregnancy test prior to receiving the first dose of study drug. 4. Willing and able to participate in all aspects of the study, including use of SC medication, completion of subjective evaluations, attendance at scheduled clinic visits, and compliance with all protocol requirements as evidenced by providing written informed consent. 	
Exclusion Criteria: Potential subjects meeting any of the following criteria will be excluded from enrollment.	

 1. Not currently enrolled in PRO 140_CD 02 or CD02_OpenLabel study 2. Any active infection or malignancy requiring acute therapy (with the exception of local cutaneous Kaposi's sarcoma) 3. Females who are pregnant, lactating, or breastfeeding, or who plan to become pregnant during the study 4. Any other clinical condition that, in the Investigator's judgment, would potentially compromise study compliance or the ability to evaluate safety measures 	
Statistical Considerations:	

Name of Sponsor:

CytoDyn, Inc.

Name of Study Product: PRO 140 (Humanized monoclonal antibody to CCR5)

Protocol Number:

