1.4.2.9 PRO 140_CD02 Study

PRO 140_CD02 study (double blind, placebo controlled, 52 subjects, multi-center) evaluated the efficacy, safety, and tolerability of PRO 140 in combination with existing ART (failing regimen) for one week and Optimized Background Therapy (OBT) for 24 weeks in patients infected with HIV-1. The study population included 52 treatment-experienced HIV-infected adult patients with CCR5-tropic virus who demonstrated evidence of HIV-1 replication despite ongoing antiretroviral therapy with documented history of genotypic or phenotypic resistance to at least one ART drug within three drug classes (or within two or more drug classes with limited treatment options). The options may be limited as a result of drug antiviral class cross-resistance or documented treatment intolerance.

In double-blind treatment period, virally non-suppressed subjects were randomized and treated with either PRO 140 or Placebo in combination with the failing ART regimen for 7 days. The primary efficacy endpoint was proportion of participants with $\geq 0.5 \log_{10}$ reduction in HIV-1 RNA viral load from baseline at the end of the 7 day functional monotherapy period.

During the 24-week open-label period, all subjects received PRO 140 along with Optimized Background Therapy (OBT).

This clinical study is completed.

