3.3 ELIGIBILITY CRITERIA

3.3.1 Inclusion Criteria

[figure not shown]
Subjects must meet all of the following criteria to be included in the study:

1. Subjects who have completed 24 weeks of treatment in PRO 140_CD 02 or CD02_OpenLabel study, and Investigator believes subject requires continued access to PRO 140 in order to continue deriving clinical benefit and maintain HIV-1 viral suppression.
2. HIV-1 RNA <50 at T23 Visit in PRO140_CD02 or CD02_Open Label study
3. Both male and female patients and their partners of childbearing potential must agree to use 2 medically accepted methods of contraception (e.g., barrier contraceptives [male condom, female condom, or diaphragm with a spermicidal gel], hormonal contraceptives [implants, injectables, combination oral contraceptives, transdermal patches, or contraceptive rings], and intrauterine devices) during the course of the study (excluding women who are not of childbearing potential and men who have been sterilized). Females of childbearing potential must have a negative serum pregnancy test at Screening visit and negative urine pregnancy test prior to receiving the first dose of study drug.
4. Willing and able to participate in all aspects of the study, including use of SC medication, completion of subjective evaluations, attendance at scheduled clinic visits, and compliance with all protocol requirements as evidenced by providing written informed consent.

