6.9.3 Change from baseline

Change from baseline will be calculated for each post baseline visit as follows:

$$\text{Change From Baseline} = \text{Post baseline result at time t} - \text{Baseline result}$$

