7.2.1 Mean change in viral load (HIV-1 RNA levels)

The raw and change from baseline in HIV-1 RNA levels (log10 copies/mL) will be summarized atleast once every four week during the treatment extension phase. For change from baseline summaries, subjects with an undefined change from baseline, because of missing data, will be excluded.

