7.2.2 Mean change in CD4 cell count

The raw and change from baseline in CD4 cell count will be summarized for each week during the treatment phase. The summary tables will include the number of observations, mean, standard deviation, median, and minimum and maximum values. For change from baseline summaries, subjects with an undefined change from baseline, because of missing data, will be excluded.

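### The SAP measures every change from the parent-study baseline, when subjects were viremic, and defines no extension-entry reference for viral load or CD4

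*SAP*

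**What the plan says.** SAP 6.1 sets a single reference for all change scores: "Baseline for a given parameter or endpoint is defined to be the baseline of CD02 or CD02_OpenLabel study". SAP 6.9.3 then applies it throughout: "Change from baseline will be calculated for each post baseline visit as follows", as the post-baseline result minus the baseline result.

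The first outcome measure in SAP 2.4 is "Mean change in viral load (HIV-1 RNA levels) at the conclusion of treatment period"; the second is the corresponding CD4 measure. Neither names its own reference point, so 6.1 governs both. SAP 7.2.1 says "The raw and change from baseline in HIV-1 RNA levels (log10 copies/mL) will be summarized", and SAP 7.2.2 says "The raw and change from baseline in CD4 cell count will be summarized for each week during the treatment phase".

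The parent baseline and extension entry differ by design. Protocol 1.4.2.9 describes the start of CD02: "virally non-suppressed subjects were randomized and treated with either PRO 140 or Placebo in combination with the failing ART regimen for 7 days". Protocol 1.4.2.10 describes the open-label parent population in similar terms, with viral replication despite ongoing therapy. Entry to the extension follows 24 weeks of PRO 140 with optimized background therapy. It requires "HIV-1 RNA <50 at T23 Visit in PRO140_CD02 or CD02_Open Label study" (Protocol 3.3.1) or "HIV-1 RNA ≤ 50 copies/ml at T23 Visit in PRO140_CD02 or CD02_OpenLabel study" (Protocol Synopsis). The difference between < and ≤ does not matter here.

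Neither document defines TE1 or T23 as a reference for change. Viral load at T1 is listed as a baseline characteristic (Protocol 8.7.2, SAP 7.1.3), but T1 is not defined in these documents and is not used to compute change.

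**The concern.** Because subjects enter suppressed, what the extension can describe is whether suppression and CD4 count are maintained. A change score anchored at a viremic time point answers another question: how far the subject has come since starting the parent study. A clearly negative mean viral-load change at the end of extension treatment fits full maintenance, and it also fits loss of suppression in many subjects. Likewise, a net CD4 gain appears whenever the loss during the extension is smaller than the gain in the parent study.

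No other planned summary clearly fills the gap. SAP 2.4 lists no proportion with virologic failure or with suppression. The disposition summary in SAP 7.1.1 need not show failures, because under Protocol 5.1 a failing subject who finishes the required follow-up counts as having completed the study.

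**Working it through.** The plan states no figure to reproduce: there is no sample size, power or expected change. The check is a decomposition with illustrative numbers.

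**Inputs**
- Entry value E: 50 copies/mL, the eligibility limit (Protocol 3.3.1 and Synopsis); 40 and 20 are used as variants.
- Rebound value V: 400 copies/mL, the virologic-failure threshold (Protocol 4; failure requires two consecutive values at or above it).
- Parent baseline B: not given in the documents. Assumed 1,000, 20,000 and 100,000 copies/mL.

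**Decomposition.** On the log10 scale:

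log10(V/B) = log10(E/B) + log10(V/E)

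The left side is the SAP change. The first term on the right is the parent-study response, fixed before the first extension dose. The second is the change during the extension. Whenever E < V < B, the SAP change is negative while the extension change is positive.

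**One subject at 400 copies/mL**

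| Reference | Formula | Change (log10) |
|---|---|---|
| Parent B = 1,000 | log10(400/1,000) | -0.40 |
| Parent B = 20,000 | log10(400/20,000) | -1.70 |
| Parent B = 100,000 | log10(400/100,000) | -2.40 |
| Entry E = 50 | log10(400/50) | +0.90 |
| Entry E = 40 | log10(400/40) | +1.00 |
| Entry E = 20 | log10(400/20) | +1.30 |

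**Where masking stops.** With B = 400 the SAP change is 0.00. With B = 1,000 and rebound to 5,000 it is log10(5) = +0.70. Rebound to or above the parent baseline is therefore not hidden.

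**Group mean.** Let a fraction f of subjects be at 400 copies/mL and the rest at 50, all with E = 50. The SAP mean is log10(50/B) + f × log10(8), and the mean from entry is f × log10(8). With B = 20,000:

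| f | SAP mean change | Mean change from entry |
|---|---|---|
| 0% | -2.60 | 0 |
| 25% | -2.38 | +0.23 |
| 50% | -2.15 | +0.45 |
| 100% | -1.70 | +0.90 |

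At f = 100%, the SAP mean runs from -0.40 (B = 1,000) to -2.40 (B = 100,000). Even with every subject at the failure threshold, the named outcome reports a reduction.

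**CD4.** The documents give no CD4 values for these subjects, so no figure is offered. The same identity holds: reported change = parent-study gain minus extension loss.

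**Values below the assay limit.** Most extension baselines will lie near or below the limit. The protocol's accounts of two sister studies report a viral load as below 40 copies/mL (1.4.2.8) or as not detectable (1.4.2.7). Under assumed codings, using 20 rather than 40 shifts a change by log10(40/20) = 0.30, and 20 rather than 50 by log10(50/20) = 0.40. Both are large beside the +0.90 above, so a new baseline needs a coding rule.

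**The case against.** The parent baseline is an explicit choice, and cumulative change since first exposure is a legitimate quantity: subjects continue the same drug and background regimen. The study is single-arm, its purpose is continued access, and SAP 7.2.4 plans no inference for safety endpoints.

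Raw log10 viral load is summarized beside the change. With entry fixed at 50, its mean is 1.70 + 0.90f, or 1.70, 1.92, 2.15 and 2.60 for f = 0, 25%, 50% and 100%. That is the change from entry plus a constant. SAP 7.1 also calls for the maximum, and all data are listed. TE1 belongs to the extension phase, so its row can probably be subtracted from later ones. Failures can also be traced: there is a dedicated failure visit, resistance and tropism results are listed by subject, and Protocol 8.7.1 summarizes reasons for discontinuation.

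Much of this stands. Rebound is not lost from the report, and the parent-baseline summary should be kept. But the named outcomes are change measures, and a raw mean is not a paired within-subject change. Subtracting rows is not paired either once numbers fall, and SAP 7.2.1 does not name TE1 as a tabulated visit. The gap is greatest for CD4, because entry values vary and eligibility does not fix them. Tracing failures through listings does not supply a pre-specified proportion.

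**Conclusion.** The concern holds. The only baseline in the SAP is a viremic one, both leading outcome measures use it, and no planned change measure isolates the extension. For a subject at 400 copies/mL, the sign of the viral-load change is wrong for the extension period under any parent baseline above 400, given entry at or below 50. The size (-0.40 to -2.40 against +0.90) rests on assumed parent baselines of 1,000 to 100,000, and the group means also rest on assumed rebound fractions. The CD4 effect has the same structure but cannot be sized from the documents. No decision rule depends on these measures, so the consequence is a reported outcome that can be misread. It should be fixed, chiefly because the fix is cheap.

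**What to change.** - In SAP 6.1, add an extension baseline: the last non-missing value before the TE1 injection. Use it for the viral-load and CD4 change measures in 7.2.1 and 7.2.2.
- State one numeric convention for HIV-1 RNA reported below the assay limit or not detected, applied identically at baseline and at every later visit.
- Keep the change from the CD02 or CD02_OpenLabel baseline alongside, labelled as cumulative change since parent-study baseline.

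The cost is SAP wording, one coding rule and one extra column in two tables. No new data are needed: HIV-1 RNA and TruCount are already scheduled at screening and before dosing at TE1 (Protocol Table 4-1, 4.2.1 and 7.11.6).

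There are limits. The viral-load change will look less favourable. TE1 coincides with the parent end-of-treatment visit and is therefore an on-drug value, which is why the cumulative summary must stay. Failing subjects move to Follow-up (Protocol 4.2) and nothing is imputed (SAP 6.3), so per-visit means will still lose them under either baseline.
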